- To evaluate if two novel treatment modalities (explained more briefly on page 9 in paragraph 'Study Onset' of chapter 'Methodology') show non-inferiority on subjective evaluations (symptom score on a Visual Analogue Scale (VAS), Therapeutic Response Evaluation (TRE) and Rhinitis Quality of Life Questionnaire (RQLQ)) compared to the current treatment modality of capsaicin nasal treatment in patients with IR. The gathered data of this single center trial can be used to guide the decision on the set-up and the design of a larger multi-center trial being powered to prove non-inferiority.

Our secondary aims are:

- To evaluate if the two novel treatment modalities show non-inferiority compared to the current treatment modality of capsaicin nasal treatment in patients with IR on objective evaluations (Peak Nasal Inspiratory Flow (PNIF) measurements before and after CDA challenge).
- To evaluate the occurrence of adverse events at week 4, week 12 and week 26 and recurrence of symptoms and NHR at week 26 in the different treatment groups.

B. Hypothesis

Non-inferiority in efficacy of the two novel treatment regimes i.e. capsaicin nasal spray 0,01mM (2puffs/nostril/day) during 4 weeks and capsaicin nasal spray 0,001mM (2puffs/nostril/day) during 4 weeks compared to the current treatment of capsaicin nasal spray 0,1mM (5/day administered on a single day) with regard to the scores on week 4 (taking into account the baseline level).

C. Outcome

- VAS for major nasal symptom at week 4, week 12 and week 26. The region of equivalence is defined as a difference in VAS of less than 1.
- VAS for total and individual nasal symptoms at week 4, week 12 and week 26. The region of equivalence is defined as a difference in VAS of less than 1.
- TRE (based on a scale from 1 to 5) at week 4, week 12 and week 26. The region of equivalence is defined as a difference in percentage for patients of less than 10% in all different TRE scoring groups.

- NHR (objectively measured by PNIF before and after CDA challenge) in all treatment modalities at week 4, week 12 and week 26. The region of equivalence is defined as a drop in PNIF of less than 10%.
- Appearance of adverse events at week 4, week 12 and week 26.
- Recurrence of symptoms (based on a scale of 1 to 5) at week 26.

Study design

A. Type of study

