- Systemic steroid treatment less than 4 weeks before the inclusion in the study, nasal steroid spray less than 4 weeks before the inclusion, oral leukotriene antagonists or long-acting antihistamines less than 2 weeks before the inclusion.
- Inability of the patient to stop taking medication affecting nasal function like β -blockers.
- History of prolonged use or abuse of decongestant nasal spray like xylometazoline spray and/or use or abuse of decongestive oral medication.
- Evidence of infectious rhinitis/rhinosinusitis or common cold within 4 weeks prior to inclusion.

- Pregnancy or lactation. **
- Any disorder of which might compromise the ability of a patient to give truly informed consent for participation in this study.
- Enrollment in other investigational drug trial(s) or receiving other investigational agent(s) for any other medical condition.
- Contra-indications for the use of local anesthesia (cocaine 5%).
- Smoking or occupational exposure to irritants (like hypochlorite, persulfates, isocyanates).
- Nasal malignancies or severe comorbidity like granulomatosis or vasculitis.

*Note *:*

Patients with underlying allergic disease are defined by positive skin prick test for the 18 most prevalent inhalant allergens (house dust mite, timothy grass, smooth meadow grass, orchard grass, nettle, plantago, oxeye daisy, mugwort, alder, birch, hazel, horse, cat, dog, rabbit, Alternaria, Aspergillus and Cladosporium - HAL Allergy, Leiden, The Netherlands) and/or positive IgE analysis in the blood.

*Note **:*

Female patients with childbearing potential will be offered a pregnancy test at the screening.

D. Possible hurdles

Based on the former studies in which the therapeutic effect of capsaicin is proven (9) (10) (11) (12) (13) (18) and given the fact that capsaicin is well tolerated and side effects are minimal, it is very unlikely to be subject of foreseen or unforeseen obstacles in the elaboration of this study protocol. Beside minor inconveniences such as rhinorrhea, sneezing and watery eyes, there are no other known side effects.

With regard to the safety of all individuals, the study will immediately be abrogated and the treatment protocol we will un-blinded at once, in case of any allergic reaction or any other adverse event.

Methodology

A. Study onset

This study will include 4 parallel arms of equal sample size.

120 IR patients will be included in this four-arm study (n=30 patients per treatment arm).

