The current study is not designed to prove non-inferiority, but serves as a pilot study to evaluate if non-inferiority is observed for the two novel treatment regimes compared to the current treatment regime. As many as possible IR patients matching the inclusion criteria (see above) will be recruited during the recruitment period. Based on previous experience in the center, the expected total number of IR patients equals 120 taking into account a recruitment period of three years. If it is possible to include 120 patients before the time frame of three years has finished, recruitment will be stopped earlier. If by any unforeseen circumstances, after three years still not enough patients are included in the study, recruitment will be running until a total number of 120 patients will be obtained.

Note:

A drop out rate of 10% due to concomitant infection, loss of follow-up or non-related adverse events is possible during the setting.

D. Statistics

A linear model for longitudinal measures (More specifically, a direct likelihood approach is adopted using an unstructured covariance matrix (Molenberghs and Kenward, 2007, Section 14.4)¹) will be used to compare the evolution of VAS, RQLQ and drop in PNIF between the four groups, with the baseline value as a covariate. A transformation of the outcome will be considered when needed to handle skewness in the distribution of the model residuals. Differences between the groups will be compared with the a-priori defined regions of equivalence (see section Outcomes). 95% confidence intervals for differences at specific time points will be reported. Note again that the aim of this pilot study is to describe the pattern of the differences, and not to prove non-inferiority based on these confidence intervals. For the evaluation of the TRE, a

¹ G. Molenberghs and M.G. Kenward. Missing Data in Clinical Studies. Hoboken, NJ : John Wiley & Sons, 2007.

logistic regression model using generalized estimating equations (GEE)² will be used to compare the evolution in proportion patients free of complaints (TRE score 5), with the baseline TRE score as covariate.

E. Patient recruitment

Patients will be enrolled by four different strategies:

- Patients with a new diagnosis of IR who visit the ENT department at the University Hospital of Leuven will be offered the possibility to take part in this study and will be screened for in- and exclusion criteria.

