Two weeks after treatment, patients will be contacted by telephone in order to evaluate adverse events, check adherence and evaluate therapeutic response.

- Follow-up visit 1 (week 4):

Nasal examination including nasal endoscopy.

NHR measurements by CDA and/or hyperosmolar discs.

Nasal fluid collection by Merocell (both nostrils) for measurement of neuromediators before and after NHR measurements.

Measurement of PNIF before and after NHR measurements.

Evaluation of the therapeutic response (TRE) on a scale from 1 (= no relief of symptoms) to 5 (= total relief of symptoms).

Symptom evaluation (VAS) for INS and TNS.

Quality of life evaluation using the RQLQ.

Evaluation of adverse events and check of adherence.

- Follow-up visit 2 (week 12):

Identical to FU 1

- Follow-up visit 3 (week 26):

Nasal examination including nasal endoscopy.

Evaluation of the therapeutic response (TRE) on a scale from 1 (= no relief of symptoms) to 5 (= total relief of symptoms).

Symptom evaluation (VAS) for INS and TNS.

Quality of life evaluation using the RQLQ.

Evaluation of adverse events and check of adherence.

	Screening week -3	Baseline week -1	Treatment week 0	FU visit 1 week 4	FU visit 2 week 12	FU visit 3 week 26
Explanation study and protocol	x					
Informed consent	x					
Evaluation in-and exclusion criteria	x	x				
Pregnancy test (if necessary)	x					
SPT (if necessary)	x					
Blood analysis	x					
ENT exam with nasal endoscopy	x	x	x	x	x	x
Nasal fluid collection		x/x*		x/x*	x/x*	
Explanation R/	x		x			
Start R/, handing over study medication and diary			x			
NHR measurements		x		x	x	
TRE				x	x	x
Symptom evaluation VAS	x	x		x	x	x
Symptom evaluation RQLQ	x	x		x	x	x
AEE and check adherence			x	x	x	x

ENT: ear, nose, throat

TRE: therapeutic Response Evaluation

AEE: Adverse Events Evaluation

*: x/x = before and after NHR measurements

Table 3: Overview of registrations and sample collections that were performed at each visit

I. Variables

- Clinical ENT exam:

Nasal endoscopy will be performed by an experienced MD.

- Skin Prick Test (SPT):

SPT for the 18 most prevalent inhalant allergens (e.g. house dust mite, grass, mugwort, alder, birch, hazel, pet animals, Alternaria, Aspergillus) provided by HAL Allergy, will be performed by investigators Apr. [name] or CTA [name].

- Blood analysis:

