Functional problems that are most troublesome to adults with rhinitis will be measured by the RQLQ by 28 questions in 7 domains (activity limitation, sleep problems, nose symptoms, eye symptoms, non-nose/eye symptoms, practical problems and emotional function). There are three 'patient-specific' questions in the activity domain, which allow patients to select three activities in which they are most limited by their rhinitis. Patients recall how bothered they have been by their rhinitis during the previous week and to respond to each question on a 7-point scale (0 = not impaired at all and 6 = severely impaired). The overall RQLQ score is the mean of all 28 responses and the individual domain scores are the means of the items in those domains. The RQLQ has excellent measurement properties and has been used extensively throughout the world both in clinical practice and clinical trials. The validation studies have shown that these properties are very similar to

those found for the Asthma Quality of Life Questionnaire (21). Patients will be asked to score RQLQ before treatment and at week 4, 12 and 26.

- Adherence evaluation:

Patients will be asked to bring their nasal spray with them on follow up visit 2 at week 4. Weighing the residual fluid on day 28 will objectively check adherence.

All patients will be asked to write down their symptoms, adverse events and degree of sensitization/desensitization in a dairy (see addendum). The diary will be handed over to them at the day of the treatment.

- Therapeutic Response Evaluation (TRE):

TRE will be measured on a 1 to 5 scale.

- 5 klachten zijn volledig verdwenen = klachtnvrij
- 4 klachten zijn bijna volledig verdwenen
- 3 klachten zijn verminderd, doch nog aanwezig
- 2 klachten zijn licht verminderd, doch nog sterk aanwezig
- 1 klachten zijn onveranderd ten opzichte van vóór de behandeling

Patients will be asked to score their symptom relief on week 4, week 12 and week 26.

- Evaluation of recurrence of symptoms:

The recurrence of symptoms will be measured on a 1 to 5 scale.

- 5 klachten zijn volledig terug aanwezig
- 4 klachten zijn voor een aanzienlijk deel terug aanwezig
- 3 klachten zijn nog steeds duidelijk verminderd
- 2 klachten zijn licht verminderd, doch beginnen terug te keren
- 1 klachten zijn nog steeds volledig verdwenen

Patients will be asked to score their recurrence of symptoms at week 26.

References

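### On the TRE alone, the lowest answer is no change, so the comparison of TRE score groups cannot separate no effect from worsening

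*Combined protocol and SAP*

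**What the plan says.** Methodology, I. Variables lists the five TRE answers in Dutch. The top one is "klachten zijn volledig verdwenen = klachtnvrij" (complaints completely gone). The bottom one, score 1, is "klachten zijn onveranderd ten opzichte van vóór de behandeling" (complaints unchanged compared with before treatment). Scores 2 to 4 are grades of improvement. The visit list in Methodology, H words the scale differently: "on a scale from 1 (= no relief of symptoms) to 5 (= total relief of symptoms").

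Objectives, A. Aims places the TRE in the primary aim together with VAS and RQLQ. Objectives, C. Outcome sets its region of equivalence as "a difference in percentage for patients of less than 10% in all different TRE scoring groups", at weeks 4, 12 and 26. Score 1 is therefore one of the groups compared between arms.

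Methodology, D. Statistics specifies one TRE model, a GEE logistic regression to "compare the evolution in proportion patients free of complaints (TRE score 5), with the baseline TRE score as covariate". It treats scores 1 to 4 as a single category.

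**The concern.** A scale that rates change from before treatment and stops at no change is cut off on the unfavourable side, which is the side that matters when asking whether a new regimen is no worse than the current one.

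The cut-off may not fall equally on the arms. Study design, D. Possible hurdles names "minor inconveniences such as rhinorrhea, sneezing and watery eyes" as effects of capsaicin, and nasal discharge and sneezing are also among the symptoms that qualify a patient for entry. Groups II and III use capsaicin daily for four weeks. Group I receives it on one day and then uses placebo. The hypothesis concerns week 4, when the daily exposure ends. If irritation did worsen symptoms in some patients, it would be more likely to show at that visit in the two novel arms, and a scale that cannot record it would favour a non-inferior reading. The documents do not say how often this happens, or whether it happens at all.

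The data are also meant to guide the design of a larger multi-center trial, so a gap in the form could be carried forward.

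**Working it through.** The plan gives no figure to reproduce here. The check maps possible patient outcomes onto the printed answers.

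**Inputs from the documents:** 30 patients per arm (Study onset); possible dropout of 10% (Sample size and setting), so 30 × 0.90 = 27 evaluable; TRE region of less than 10% in each score group; VAS region of less than 1.

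**Assumptions:** all rates of worsening, the VAS standard deviation, that worsened patients tick 1, and that the VAS has room above the entry threshold of 5.

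**Step 1. What the printed scale shows.** Three constructed arms of 30:

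| | Worse | Unchanged | Score 2 | Score 3 | Score 4 | Score 5 | Recorded as score 1 |
|---|---|---|---|---|---|---|---|
| Arm A | 0 | 12 | 6 | 6 | 3 | 3 | 12/30 = 40% |
| Arm B | 9 | 3 | 6 | 6 | 3 | 3 | (9 + 3)/30 = 40% |
| Arm C | 9 | 12 | 3 | 3 | 2 | 1 | (9 + 12)/30 = 70% |

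Arms A and B have the same recorded distribution for scores 1 to 5, 40/20/20/10/10%. The difference is 0 in every group, although 9/30 = 30% worsened in B and none in A. In arm C the worsening displaces responders instead: score 1 is 70 − 40 = 30 points above arm A, and the region is breached. Even then the TRE does not show whether the extra patients at score 1 were unhelped or made worse.

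**Step 2. What a separate answer would show.** A against B becomes 0% versus 30% worse and 40% versus 3/30 = 10% unchanged. The share at score 5 stays at 3/30 = 10% in both arms, so the GEE comparison of A with B is the same as before.

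**Step 3. What the VAS would show.** If 30% of an arm worsens by w points and the other patients match the comparator arm, the arm mean shifts by 0.30 × w:

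- w = 1, 2, 3, 4 gives 0.3, 0.6, 0.9, 1.2, against a region of 1.
- The 95% half-width for a difference between two arms is 1.96 × SD × √(2/27). This is 0.80 for SD 1.5 and 1.60 for SD 3.

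The VAS therefore registers the worsening, but a sizeable minority who worsen by up to 3 points can leave the mean difference inside the region, and the estimate is imprecise.

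**Step 4. Precision of the added category.** At assumed worsening rates of 10%, 15% and 20%, 27 patients give 2.7, 4.1 and 5.4 worsened per arm. With 10% worse in both arms, the 95% half-width for the difference is 1.96 × √(2 × 0.10 × 0.90/27) = 0.16, or 16 points, against a region of 10. Three patients against none is 3/27 = 11%, which already exceeds it.

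**The case against.** A reader might infer that an aggravating regimen would look the same in this trial as one that does nothing. The documents do not support that. VAS and RQLQ stand in the same primary aim, are scored before treatment and at weeks 4, 12 and 26, and are modelled with baseline as covariate, so both can move in the unfavourable direction. Adverse events are evaluated from week 0 onward, a telephone call at two weeks covers adverse events and response, and patients keep a diary of symptoms and adverse events. The share of patients whose total nasal symptom VAS rose can be counted from data already planned.

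A reader might also infer that worsened patients are certain to be entered as unchanged. The documents give no scoring rule. Under the wording in the visit list, a worsened patient has had no relief and score 1 is a correct answer; the item may also be left blank.

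It is fair to add that the TRE is presented as a relief scale, that the only specified TRE model ignores the distinction, that exact masking needs worsening to be offset by fewer unchanged patients, and that the named drug effects are described as minor, with no statement that they persist or exceed baseline symptoms. The study is a pilot that does not set out to prove non-inferiority.

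All of this stands, and it limits the point. It does not remove it. The Outcome section applies the region to every TRE score group, including score 1, and that group can mix two different results. The planned VAS and RQLQ analyses compare group evolution and not the share who worsened, RQLQ has no region in the Outcome list, and no diary analysis is described.

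**Conclusion.** The point holds, limited to the TRE. The five printed answers offer nothing below unchanged, the two descriptions of score 1 differ, and there is no rule for a worsened patient. As a result, the comparison of TRE score groups cannot separate no effect from aggravation.

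The effect is modest. It touches a descriptive comparison in a pilot and leaves the GEE result and the VAS and RQLQ analyses as they are. In the least favourable constructed case, a 30-point difference in worsening appears as 0 on the TRE. That case rests on assumed rates, on worsened patients ticking 1, and on an exact offset between worse and unchanged. Where worsening displaces responders, the comparison shows a difference but not its nature.

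**What to change.** - Add one answer below score 1, stating that complaints are worse than before treatment, at weeks 4, 12 and 26.
- Report its percentage by arm within the descriptive comparison of TRE groups. Also report it combined with score 1, so that the 1 to 5 scale is preserved.
- Use the same wording for score 1 in the visit list and in the Variables section.
- If forms are already in use, report by arm the share of patients whose total nasal symptom VAS is above baseline, from data already collected. Small rises may be measurement noise, so set these shares beside the placebo arm.

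The cost is one line on the form and one row in a table. At about 27 patients per arm the intervals will be wide, so the text should say that the added row is descriptive and supports no non-inferiority claim.

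### The week-26 recurrence scale is out of order at scores 2 and 3 as worded, and the item is missing from the week-26 visit list and Table 3

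*Combined protocol and SAP*

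**What the plan says.** Recurrence at week 26 is a listed outcome (Objectives, C. Outcome). It is also part of a secondary aim (Objectives, A. Aims), which covers "recurrence of symptoms and NHR at week 26 in the different treatment groups".

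The only definition is in Methodology, I. Variables, under the evaluation of recurrence of symptoms. The ends of the scale are "1 klachten zijn nog steeds volledig verdwenen" (still completely gone) and "5 klachten zijn volledig terug aanwezig" (fully back). Score 4 means that complaints are back to a considerable extent. Between 1 and 4 stand "3 klachten zijn nog steeds duidelijk verminderd" (still clearly reduced) and "2 klachten zijn licht verminderd, doch beginnen terug te keren" (slightly reduced, but beginning to return). The section closes with an instruction: "Patients will be asked to score their recurrence of symptoms at week 26".

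Methodology, H. Time schedule and visit table describes the week-26 visit as nasal examination with endoscopy, TRE, VAS, RQLQ, adverse events and adherence. It lists no recurrence score. "Table 3: Overview of registrations and sample collections that were performed at each visit" has no recurrence row either.

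Methodology, D. Statistics names a longitudinal linear model for VAS, RQLQ and drop in PNIF, and a GEE logistic model for TRE. It names no summary, model or cut for recurrence.

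**The concern.** The end anchors say that a higher score means more recurrence. The wording of 2 and 3 runs the other way: a patient who is only slightly better and relapsing is offered a lower number than one who is still clearly better. Any summary that relies on the order of those two numbers then mixes two meanings. Because Statistics fixes no summary for this item, nothing in the plan steers the analyst to one that is safe.

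The second issue is collection. The objectives and the variable definition call for the score at week 26, but the two visible schedules that staff would work from do not list it. TRE does not stand in for it, because TRE is a separate scale with its own definition.

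Both issues bear on the one item that measures recurrence directly, in a trial whose stated purpose is to describe patterns of difference between arms.

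**Working it through.** **Order of the labels.** By meaning, from least to most recurrence:

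| Meaning | Printed score | Rank by wording |
|---|---|---|
| completely gone | 1 | 1 |
| clearly reduced | 3 | 2 |
| slightly reduced, returning | 2 | 3 |
| back to a considerable extent | 4 | 4 |
| fully back | 5 | 5 |

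Only the pair 2/3 is inverted. The TRE scale in the same section supports reading *licht verminderd* as the worse state: there, slightly reduced (2) is a poorer result than reduced (3). Each number carries its own label, so text extraction is an unlikely cause.

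**Effect on a mean, if the wording order is the intended one.** Printed coding gives each clearly-reduced patient one point more than the wording rank and each returning patient one point less. So, for arms A and B:

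(printed difference B-A) - (wording-order difference B-A) = (B-A difference in share clearly reduced) - (B-A difference in share returning).

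**Inputs for the illustrations.** The plan gives 30 patients per arm (Study onset) and calls 10% dropout possible (Sample size and setting, note): 30 × 0.90 = 27. It gives no distribution of the score, so the counts below are assumed. They are listed as gone / clearly reduced / returning / considerable / fully back.

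- (a) A 5/11/5/3/3, B 5/5/11/3/3: arms differ only in the 2/3 split.
- (b) A 8/11/3/3/2, B 3/8/8/4/4: arms differ throughout.
- (c) A 11/5/5/3/3, B 5/5/5/6/6: no difference in the middle categories.

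Means, total score over 27:

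- (a) Wording order: 69/27 = 2.556 vs 75/27 = 2.778. Printed: 75/27 = 2.778 vs 69/27 = 2.556.
- (b) Wording order: 61/27 = 2.259 vs 79/27 = 2.926. Printed: 69/27 = 2.556 vs 79/27 = 2.926.
- (c) 63/27 = 2.333 vs 84/27 = 3.111 under both.

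SE = √(s²_A/27 + s²_B/27), with Welch t intervals:

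| Case | B-A, wording order (95% CI) | B-A, printed (95% CI) | Score ≥3, wording order, A vs B | Score ≥3, printed, A vs B |
|---|---|---|---|---|
| (a) | +0.22 (-0.45 to 0.90), SE 0.336 | -0.22 (-0.90 to 0.45), SE 0.336 | 11/27 vs 17/27 | 17/27 vs 11/27 |
| (b) | 0.67 (-0.01 to 1.34), SE 0.336 | 0.37 (-0.31 to 1.05), SE 0.339 | 8/27 vs 16/27 | 16/27 vs 16/27 |
| (c) | 0.78, SE 0.390 | 0.78, SE 0.390 | 11/27 vs 17/27 | 11/27 vs 17/27 |

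Check against the rule: (a) -6/27 - 6/27 = -0.444; (b) -3/27 - 5/27 = -0.296; (c) 0 - 0 = 0. These equal the changes in the table.

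**Summaries that do not depend on the order of 2 and 3.** Score ≥4 is the same under both codings: (a) 6/27 vs 6/27, (b) 5/27 vs 8/27, (c) 6/27 vs 12/27. So is score 1: (a) 5/27 vs 5/27, (b) 8/27 vs 3/27, (c) 11/27 vs 5/27. In case (a) neither cut shows the difference between the arms, which only the full five-category table displays.

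**The case against.** **The harm needs an analysis that the plan does not contain.** This stands. No mean, rank test, ordinal model or cut is specified for recurrence. A reader might infer that the planned recurrence comparison is wrong; the documents support only that an unplanned choice could make it so.

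**The intended order is unknown.** This also stands. A reader might infer that 2 and 3 were simply exchanged and should be recoded. But beginning to return can be read as early recurrence, which fits next to score 1, and then *licht* would be the slip. Under that reading, or if patients answer by number position, the printed codes may already be in the intended order, and the reversal and dilution figures would not measure an error. At least one label still needs correcting.

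**The examples are constructed.** Case (a) is the pattern that gives a pure sign flip, and the intervals in (a) and (b) include zero under both codings. They show what is possible, not what is likely. No change in statistical significance is claimed.

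**The omission may be only apparent.** Table 3 calls itself an overview and also leaves out the two-week telephone contact. Table 2, the patient form and the diary addendum are not visible. A reader might infer that the score will not be collected. That goes too far, because the variable definition expressly instructs collection at week 26. What stands is that the visible schedules disagree with it.

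**Conclusion.** The point holds on two facts that can be read from the text: as worded, labels 2 and 3 run against the anchors at 1 and 5, and the week-26 visit list and Table 3 omit an item that the objectives and the variable definition place at week 26.

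The effect on results is conditional. It requires that the wording order is the intended one, that the analyst picks an order-dependent summary, and that the arms differ in categories 2 and 3. With the assumed counts, the mean difference then moves by 0.44 or 0.30 points, or not at all.

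The weight is minor, though worth correcting: a secondary outcome in a pilot that aims to describe and not to prove, with the week-4 hypothesis untouched and with TRE, VAS and RQLQ all scheduled at week 26. Confidence is high for the label and schedule facts, and lower for any consequence in the results.

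**What to change.** 1. Confirm the intended labels with the sponsor. Correct the definition in Methodology, I. Variables and any patient form, so that the five labels are monotone.
2. Add the recurrence score to the week-26 visit list and as a week-26 row in Table 3, and check Table 2 for the same entry.
3. Add to Methodology, D. Statistics that recurrence at week 26 is reported by arm as a five-category table. If a single cut is also wanted, use one that does not depend on the order of 2 and 3 (score 1 against 2 or more, or score 4 or more), chosen before unblinding. Read it alongside TRE: the definition does not restrict the item to patients who had improved, so patients who never responded may also score high.
4. If forms with the printed labels have already been completed, check their wording and keep the five-category table as the main result. Show any order-dependent summary under both codings, as sensitivity analyses. Do not recode by default.

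The cost before use is corrected labels, one line in the visit list, one table row and a short addition to Statistics, with no data beyond what the protocol already calls for. After use it is one table and, if wanted, two sensitivity codings. Neither coding can recover answers that patients gave by number position, which is the reason to correct the labels early.
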